## **8. RESOURCES**

This study will take place at the CRIU. Study sessions will only be conducted on weekdays. All drug administration will take place at the UK CRIU in a room equipped with all the necessary physiologic and computer equipment for the study. [name] is an adult psychiatrist who has worked extensively with individuals with substance use disorders in both the clinical and research setting and he is the responsible medical investigator for this study. [name] is a psychiatrist who has worked extensively with individuals with substance use disorders in both the clinical and research setting and he is the back up medical investigator for this study. They will be available to attend to medical problems as well as any psychological or psychiatric issues that may arise. [name] will provide scientific oversight for the study and have safely completed numerous human behavioral pharmacology studies. Overall, the study team and resources described above are well equipped to protect subjects and successfully implement, carry out and complete this study protocol.

## **9. POTENTIAL RISKS**

The self-administration measure, subjective drug-effect questionnaires, performance and physiological measures employed in these studies are benign. The risks to the study subjects are those related to the ingestion of the drugs under study. All of the drugs to be administered in the proposed research are commercially available. The relative safety as well as the contraindications and possible side effects of these compounds are well known and documented. However, the administration of any drug involves some risks simply because individuals differ in their reactions to drugs. The main risk is that subjects will experience side effects that may be unpleasant.

Common side effects of COC and PHEN include nervousness, restlessness, faintness, irritability, shaking, nausea, headache, flushing, increased urine production, sweating, performance impairment, rash, blurred vision, irritation in nose and throat (due to intranasal insufflation of COC only), difficulty sleeping, loss of appetite, weight change and changes in heart rate or blood pressure. More serious side effects following the chronic, unsupervised administration of much higher doses of cocaine have occurred and include arrhythmias, psychotic episodes, suppressed breathing, seizures, myocardial infarctions, heart failure and death.

These side effects may be more frequent and larger in magnitude when testing the COC-PHEN combinations.

The doses to be administered in the present experiment were chosen to minimize, if not eliminate, the chance of these side effects occurring since these side effects are related to dose. Thus, it is unlikely that subjects will experience side effects during the experimental protocol. All sessions proposed in this application will be conducted at the CRIU and under medical supervision. Side effects of the drugs are temporary, usually dissipating in less than 24 hours. The principal investigator on this project, [name], has had extensive experience over the last 15 years administering therapeutic and supratherapeutic doses of stimulant drugs to subjects in both inpatient and outpatient settings and has never observed a serious, unexpected adverse effect. [name] will train all staff on this project.

To avoid potential drug interactions, subjects taking any prescribed medication chronically, except birth control, will be excluded. The medical personnel on this protocol will determine if it is safe for a potential subject to discontinue taking their medication during their participation.

There is some theoretical risk that subjects might choose to seek out illicit sources of drugs they received experimentally and liked. However, this risk is minimal since all drugs are administered under blind conditions and in a setting that is not conducive to the development of dependence.

## **10. SAFETY PRECAUTIONS**

Subjects are carefully screened (history and physical exam, routine labs such as CBC, complete metabolic panel and urinalysis, ECG and psychiatric assessment) to exclude those with potential increased risk of adverse effects, such as personal or first degree family histories of heart disease, histories of seizure or head injury associated with more than a brief loss of consciousness, hypertension, psychosis, etc. During sessions subjects remain under careful medical observation and

are monitored continuously by on-site medical staff. Vital signs will be collected throughout the dosing period. Staff is familiar with the acceptable physiological parameters for these studies and this information is posted in every experimental session room. In addition, [name] has substantial experience administering medications to human subjects under a variety of dosing conditions. Lastly, female subjects are also given pregnancy tests prior to each session to ensure that we do not administer active medications to a pregnant woman.

**Legal risks including loss of confidentiality:** All intake documentation that contains personal information is handled separately from the actual data collected during the study. All information of a personal nature (intake assessments, medical test results) is kept locked either on password-protected computers or in secure filing cabinets all behind locked doors and accessible only to key personnel involved in the research. A Certificate of Confidentiality will be obtained from NIDA.

## **11. BENEFIT vs. RISK**

The degree of risk to which individual study subjects are exposed as a consequence of their research participation is slight. In contrast, the potential and probable benefits to be derived by society in general and by patients as a group appear to be considerable. The major benefits of this study are clinical and scientific ones related to the knowledge gained about putative medications for COC use disorders. The data from this project will contribute to a better understanding of drug abuse and will ultimately contribute to the development of improved prevention, control and treatment procedures. Individual study subjects are expected to benefit personally from the medical and psychiatric evaluations and from referrals for medical and psychiatric treatment that are provided whenever appropriate. Overall, the risk/benefit ratio appears favorable and the conduct of this research seems well justified.

## **12. AVAILABLE ALTERNATIVE TREATMENTS**

There are no available alternative treatments as this is not a treatment study. If subjects express the desire for treatment they will be given referrals for treatment and not be allowed to participate in this study.

## **13. RESEARCH MATERIALS, RECORDS AND PRIVACY**

Urine and blood samples will be collected at screening prior to a subject's participation in the experimental protocol under another IRB approved protocol (Number 03-0509). These urine samples will be tested for the presence of a full range of drugs of abuse. Blood samples will be used for the laboratory chemistries. Females will also be given a pregnancy test at the time of screening (via the urine sample). Urine drug and pregnancy tests will be conducted prior to the conduct of each experimental session. Other data obtained from the subjects will involve subjective effects based on questionnaires, various computer-based tasks and non-intrusive staff observations and ratings. The consent form states that subject's confidentiality will be protected.

## **14. CONFIDENTIALITY**

Identifying information will be stored in a separate, locked area from all other de-identified data and codes linking the two will be kept under lock and key or on password protected computers. Incidental materials containing subject identifiers will be shredded or incinerated. Identification and access of identified data/specimens will be available only to study investigators when it is detrimental to subject safety or the conduct of the research protocol. For example, if a subject has an adverse event, we will want to obtain a quantitative drug screen to identify whether there may have been illicit drug use while in the study versus a true adverse event related to the study procedures. In the future, data/specimens may be shared with non-UK affiliations in a HIPAA compliant manner.

## **15. PAYMENT**

Subjects will be paid \$40 for each day they reside on the CRIU and will receive a \$40 completion allowance for these days if they complete the entire experiment. Subjects can also earn an additional \$2.50 during each experimental session depending on how they distribute choices for drug and money. Any money earned in experimental sessions will be added to their overall payment. The amount earned by the subject will be disbursed to them upon completion of the study. Payments will be disbursed in amounts up to \$500 dollars and will be given once per week following discharge until the subject is paid in full. When subjects return on a weekly basis to receive their payments, we will survey them regarding

their drug use since being discharged from the study. A subject can earn approximately \$2660 for participating in this study.

## **16. COSTS TO SUBJECTS**

There will be no cost to the subject for participating. Costs for the screening procedures (i.e., medical history questionnaire, physical examination including laboratory chemistries (blood chemistry screen, complete blood count, urinalysis) and a psychiatric examination will be paid by the Laboratory of Human Behavioral Pharmacology.

## **17. DATA AND SAFETY MONITORING**

### *Data Monitoring Plan*

Data will be collected using a computerized data collection and management system wherever possible. This system automates the collection of data, which ensures the accuracy and completeness of data collection. The data are stored in a unique file on the hard drive of the computer and are printed after all the tasks are completed. In all instances, the data files do not contain the name of the subject, but instead, each subject is identified by a unique four-digit number. A computer file linking the unique number with the subject's name will be kept on a stand-alone, password-protected computer. All data requiring hand entry (e.g., cardiovascular measures) will be entered by two separate staff members and comparison macros will be run to ensure accuracy. Data files for experimental tasks and physiological measures from each experimental session will be manipulated and combined into a single electronic spreadsheet for each subject by one of the investigators. Data for all subjects will then be combined into a single electronic spreadsheet and separated by experimental measure for statistical analysis using SPSS (IBM, Armonk, NY).

In this protocol the primary outcome measure will be the influence of PHEN maintenance on the reinforcing effects of COC. The alpha level will be set at 5%.

As noted above, wherever possible, data are collected using an automated computer system, which increases the accuracy and completeness of data collection and ensures the validity and integrity of the data. The initial data manipulation described above will be conducted twice and compared. The quality of manipulated data and data analyses will be monitored by random inspection by the PI and/or Co-Investigators.

### *Safety Monitoring Plan*

Potential subjects will provide information regarding their drug use history and undergo an extensive physical and psychiatric health screening to determine their eligibility and safety of their participation. Any potential subject with a history of clinically significant physical disease, current physical disease (e.g., impaired cardiovascular functioning, histories of seizure, head trauma or CNS tumors) or current or past histories of psychiatric disorder that in the opinion of the study physician would interfere with study participation, other than substance abuse or dependence, will be excluded from research participation. Females must be using an effective form of birth control in order to participate and must not be pregnant. Methods for monitoring adverse events (AEs) will include observations by the medical and research staff, spontaneous report by the subjects and, regular measurement of cardiovascular function. Subjects will not receive study drug if they have any signs or symptoms that may contraindicate its administration (e.g., HR and BP outside of predetermined range, development of serious side effects).

All AEs occurring during the course of the study will be collected, documented and reported to the PI. The occurrence of AEs will be assessed for the duration of participation. Each week a study investigator will review the AE forms from the previous week for events that were reported as new or continuing. The study investigators will follow all AEs to the point of a satisfactory resolution. Subjects may be withdrawn from the study if the medically responsible investigator determines it is the best decision in order to protect the safety of the subject. All AEs will be assessed to determine if they meet criteria for a serious adverse event (SAE).

Serious Adverse Events, as defined by the FDA, will be systematically evaluated for the duration of participation and during the follow-up visits at 2 and 4 weeks following study completion. Any SAE,

whether or not related to the study drug, will be reported to the IRB, CRIU, NIDA and the FDA. The initial SAE report will be followed by submission of a completed SAE report to all three institutions.

In the event that a subject either withdraws from the study or the investigator decides to discontinue a subject due to an SAE, the subject will have appropriate follow-up medical monitoring. Monitoring will continue until the problem requiring hospitalization has resolved or stabilized with no further change expected, is clearly unrelated to the study drugs or results in death. Outcome of SAEs will be periodically reported to IRB, CRIU, NIDA and the FDA. A summary of the SAEs that occurred during the previous year will be included in the annual progress report to NIDA, the IRB, CRIU and FDA.

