## 7. RESEARCH PROCEDURES

*General Procedures.* Subjects that meet the inclusion criteria will participate as inpatients at the University of Kentucky CCTS Research Inpatient Unit (CRIU). Subjects will be discharged upon completion of the entire protocol.

This experiment will require each subject to participate for approximately five weeks. Experimental sessions will be conducted as outlined in Table 1 below. We would like to note that COC doses will both be given in random order, whereas order of PHEN dosing will be counterbalanced across subjects. We would also like to note that subjects may be maintained on a given PHEN condition for more than 11 days prior to session to avoid testing COC doses on weekends.

Day	Table 1. Experimental Procedures
1	Admission to the CRIU.
2	Practice Session.
3-17	Placebo maintenance. Placebo administered twice daily (0700 and 1900 hours).
14-17	Experimental Sessions. Reinforcing effects of intranasal COC (0 [placebo], 20, 40 and 80 mg) determined using progressive-ratio procedure.
18-32	PHEN maintenance. Administered in divided doses (0700 and 1900 hours). Subjects receive 35 mg twice daily for two days, then 70 mg twice daily for two days, then 105 mg twice daily for remainder of maintenance period.
29-32	Experimental Sessions. Reinforcing effects of intranasal COC (0 [placebo], 20, 40 and 80 mg) determined using progressive-ratio procedure.
33	Discharge

During their participation in the research protocol, subjects will not be allowed to leave the CRIU, nor will visitors be allowed, with the exception that subjects can leave for walks under clinical supervision and if approved by physicians. Research subjects will be allowed to make local telephone calls. After completing the research protocol, interested subjects will be offered a referral to an appropriate drug abuse treatment program.

All subjects will provide urine and expired air samples before and periodically during study participation. The presence of non-nicotine drugs of abuse or alcohol not administered experimentally in the research protocol will result in immediate termination from the research study.

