Subjects will be excluded from further research participation if at any time during the experimental sessions COC increases heart rate above 130 bpm, systolic pressure above 180 mmHg, diastolic pressure above 120 mmHg or if clinically significant and/or prolonged ECG abnormalities are noted. Subjects will remain seated for the duration of the experimental session. Between the sampling and self-administration phases, subjects will be allowed to eat a standard hospital lunch but will not be allowed to smoke. No experimental activities will be scheduled for the remainder of the day after a self-administration session, but subjects will receive their appropriate maintenance medication at 1900 hours. Subjects will be free to engage in recreational activities (e.g., watch television, read, listen to music, arts and crafts, play video or board games). Research subjects will be required to be in bed with the lights out by 2300 hours.

Time	Table 2-Daily Activities for Maintenance Days
0700	Patient awakened. Vital signs recorded. Medication administered if vitals are within range and no indication of sedation or withdrawal. Subject eats breakfast.
1200	Lunch is served.
1300	UKU completed.
1900	Dinner is served. Vital signs recorded. Medication administered if vitals are within range and no indication of sedation or withdrawal.
2300	Lights out.

Time	Table 3-Daily Activities for Experimental Days
0700	Patient awakened. Vital signs recorded. Medication administered if vitals are within range and no indication of sedation or withdrawal. Subject eats breakfast.
0900	Vital signs recorded. Computerized tasks completed. ECG monitoring begins.
0930	Vital signs recorded. 0 [placebo], 20, 40 or 80 mg intranasal COC administered if vitals are within range. Measures completed 0, 15, 30, 45 and 60 minutes after drug administration.
1030	Sampling phase ends.
1200	Lunch is served.
1300	UKU is completed.
1330	Vital signs recorded. Computerized tasks completed (including progressive-ratio task). ECG

	monitoring begins.
1430	Vital signs recorded. Portion of intranasal dose earned is administered if vitals are within range. Measures completed 0, 15, 30, 45 and 60 minutes after drug administration
1530	Session ends. Remainder of daily activities identical to those listed in Table 2.

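### Non-serious adverse events that start after discharge have no planned collection, so observation after the last PHEN dose is about a day in the placebo-first order and 15 inpatient days in the PHEN-first order

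*Combined protocol and SAP*

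**What the plan says.** **Adverse-event window.** Section 17, Safety Monitoring Plan: "The occurrence of AEs will be assessed for the duration of participation". Serious events are evaluated over that same period and also "during the follow-up visits at 2 and 4 weeks following study completion". Events already reported are followed until they resolve.

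**Dosing and discharge.** Table 1 in section 7 shows the placebo-first order. PHEN runs from day 18 to day 32, rising in steps and "then 105 mg twice daily for remainder of maintenance period". Days 29-32 are also cocaine session days, and section 7 says that after a session "subjects will receive their appropriate maintenance medication at 1900 hours". The day-33 row lists discharge and nothing else. The general procedures add: "Subjects will be discharged upon completion of the entire protocol".

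**Side-effect scale.** The UKU is to be completed daily. Tables 2 and 3 both place it at 1300.

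**Order.** Section 7 states that PHEN order is counterbalanced across subjects. No washout is scheduled between the two maintenance periods.

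**Contact after discharge.** Section 15 says that payments "will be given once per week following discharge until the subject is paid in full". At those visits subjects are surveyed about drug use; adverse events are not mentioned.

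**The concern.** The serious-event sentence names the 2- and 4-week visits in addition to participation, so participation as used there ends before those visits. General adverse-event collection therefore appears to stop at discharge.

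In a crossover this stopping point does not fall equally on the two orders. Subjects who take PHEN second leave the unit about a day after their last dose. Subjects who take it first remain under daily inpatient monitoring for two further weeks. Any non-serious event that begins some days after the last PHEN dose can be seen in one order and has no planned route into the record in the other.

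What is at stake is the completeness of the safety description of PHEN combined with cocaine. Section 9 itself warns that side effects may be more frequent and larger with the combination. The reinforcement outcomes are not at stake.

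**Working it through.** The check is schedule arithmetic. No sample-size or error-rate formula is involved.

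**1. Length of stay, reproduced from the plan's own payment figure.** Section 15 gives $40 per inpatient day, a further $40 per day for completion, and up to $2.50 per session; section 7 gives 8 sessions.
- 33 days: 33 × $40 + 33 × $40 + 8 × $2.50 = $1320 + $1320 + $20 = $2660, the stated total.
- 32 days: 32 × $80 + $20 = $2580, which does not match.

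The stay is 33 days, which agrees with discharge on day 33.

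**2. Placebo-first order (Table 1).**
- Titration: 35 mg twice daily on days 18-19, 70 mg on days 20-21, 105 mg from day 22. This gives 29 − 22 = 7 days at target before the first session, as the plan says.
- Last scheduled PHEN dose: 1900 on day 32, if vital signs are in range.
- Last tabulated UKU: 1300 on day 32, before both the earned cocaine dose (1430, Table 3) and the last PHEN dose (1900).
- Discharge: some time on day 33. Hours after the last dose = (24 − 19) + discharge hour, so 5 h at the start of day 33 and 29 h at its end.

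The systematic scale has no tabulated reading after the last PHEN dose. Staff observation and spontaneous report cover the 5 to 29 hours that remain.

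**3. PHEN-first order (Table 1 with the two periods exchanged).**
- Last PHEN dose: 1900 on day 17.
- First placebo dose: 0700 on day 18, 12 hours later.
- Inpatient placebo days: 32 − 18 + 1 = 15, each with a UKU and staff observation.

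**4. Side by side, after the last PHEN dose.**

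| | Placebo-first | PHEN-first |
|---|---|---|
| Inpatient observation | 5-29 h | 15 full days, then to discharge |
| Tabulated UKU readings | none | 15 |
| New non-serious events after discharge | not collected | not collected |
| Serious events, 2 and 4 weeks after discharge (days 33 + 14 = 47 and 33 + 28 = 61) | sought | sought |

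**5. Subjects affected.** 36 ÷ 2 = 18 completers in the placebo-first order if the split is equal.

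**6. Visits already available.** $2660 ÷ $500 = 5.32, so about 6 weekly payment visits follow discharge for a subject who earns the full amount.

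**The case against.** Several points on the other side stand.

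- **Much is still captured.** Serious events are sought at 2 and 4 weeks, events open at discharge are followed to resolution, and subjects stay on the unit overnight after the last evening dose. It would be wrong to say that the effects of the last dose go unrecorded. The gap is new, non-serious events that first arise after discharge.
- **The tolerability hypothesis concerns active maintenance.** Section 1 hypothesises that cocaine is well tolerated while subjects are on PHEN. Both orders have the same scheduled maintenance days and cocaine sessions for that. Events after PHEN stops bear on the hypothesis only indirectly.
- **No stopping effects of PHEN are described.** The plan gives no rate or type of event to expect, so only the number of subjects affected can be stated, not the number of events missed.

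Two stronger readings are tempting, and the documents support neither. A reader might infer that, in the PHEN-first order, events after stopping are counted against placebo, and that together with the missed events this makes PHEN look safer. But the plan contains no rule for assigning an event to a condition and no table of adverse events or UKU scores by condition, so neither the assignment nor a direction of bias can be shown.

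A reader might also see a conflict between the day-33 discharge and section 9, which says: "Side effects of the drugs are temporary, usually dissipating in less than 24 hours". That is a general description of risk, qualified by the word for what is usual. It sets no observation period, and a discharge within 24 hours of a dose does not contradict it.

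The objection that this is only a point for clarification does not fully succeed. The collection window is a stated rule, and applied to the stated schedule it gives unequal ascertainment by order.

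**Conclusion.** The point holds in a limited form. The stated adverse-event window leaves new non-serious events after discharge uncollected. Because PHEN is the last treatment in one order and the first in the other, observation after the last PHEN dose is 5 to 29 hours in one and 15 inpatient days in the other. About half the subjects are affected, 18 of 36 under an equal split.

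This rests on three assumptions: counterbalancing means roughly equal numbers per order, which the plan implies but does not state as a figure; the PHEN-first calendar mirrors Table 1; and the final doses are given as scheduled. Section 7 allows longer maintenance to avoid weekend sessions. That would shift the calendar days without removing the difference between orders.

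The primary analysis of break point and doses earned is unaffected. This is an inexpensive improvement to the safety data, not an error that threatens the trial's main conclusion.

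**What to change.** In the Safety Monitoring Plan, extend collection of all adverse events, not only serious ones, to visits that the protocol already schedules after discharge: at least the first weekly payment visit (section 15), and the 2- and 4-week follow-up visits. State one window after the last PHEN dose, the same length in both orders. In the PHEN-first order it falls within the inpatient placebo period; in the placebo-first order it runs past discharge to the visits.

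Add one sentence saying that, if adverse events are listed by maintenance condition, events that start in that window are flagged as post-PHEN in both orders. The medical investigator should set the length of the window. No change to dosing or discharge is asked for.

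The cost is a few extra questions at visits that take place anyway, and somewhat more adverse-event records to review. The resulting safety picture may be less favourable to PHEN.
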